### 10.0 ADVERSE EVENTS AND UNANTICIPATED ADVERSE DEVICE EFFECTS

An Adverse Event (AE) is defined as any untoward medical occurrence in a patient whether or not related to the medical device or procedure. Adverse Events will not be captured unless they are study related or the relationship is unable to be determined.

An Adverse Device Effect (ADE) is a study-related Adverse Event. Adverse Device Effects (ADEs) that occur during the study will be captured on an Adverse Event Form

and reported to the Sponsor. If the relationship of the adverse event to the System is not able to be determined, it will be captured on an Adverse Event Form and reported to the Sponsor. Specific details regarding the ADE, including the event category, severity of event, and seriousness will be collected. Any necessary treatment or intervention required and the resolution status of the ADE will also be documented. ADEs will be followed to resolution. Any ADEs that meet the requirements for Medical Device Reporting (MDR) will be entered into SPR's complaint system.

All ADE's are further categorized as anticipated or unanticipated. Any ADE's specified in the Risk Analysis of this Study Plan will be considered "anticipated". All other ADE's are considered "unanticipated". Anticipated events that occur with a greater frequency than expected are also considered unanticipated.

An Unanticipated Adverse Device Effect (UADE) is defined as any serious adverse effect on health or safety or any life threatening problem or death caused by, or associated with, a device, if that effect, problem or death was not previously identified in nature, severity or degree of incidence in this Study Plan or application or any other unanticipated serious problem associated with a device that relates to the rights, safety or welfare of subjects.

[figure not shown]

Table 2: Unanticipated Adverse Device Event Sponsor Contact Information

	UNANTICIPATED ADVERSE SPONSOR CONTACT IN	DEVICE EVENT	
Name/Title	Email address	Telephone Number	Fax Number

It is the responsibility of the investigator to inform his/her Institutional Review Board (IRB) of any ADEs and UADEs as required by the IRB. In addition, some IRBs will require that AEs that are serious in nature, even if not study related, will be reported as well. SPR Therapeutics is responsible for furnishing the required information to the appropriate regulatory authorities.

Deficiencies related to the identity, quality, durability, reliability, usability, safety or performance of a device should be reported to SPR promptly. Sites will be provided with instructions for the reporting of device complaints in accordance with SPR's standard operating procedures.

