### 9.5 Independent Clinical Events Reviewer

An Independent Clinical Events Reviewer (ICER) will be utilized for this study to adjudicate study related adverse events (AEs). AE information, including group assignment, will be provided to the Reviewer. The adjudication by the Clinical Events Reviewer will be the final determination.

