### 9.1 Adverse Device Effects

Adverse device effects (ADEs) will be reported and an overall summary of the number and percentage of subjects with at least one ADE, serious ADE, unanticipated ADE, or ADE leading to death will be presented by treatment group.

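### Adverse events judged unrelated are not recorded, so the by-group safety comparison rests on an attribution made before capture that the independent reviewer cannot revisit

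*Protocol*

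**What the plan says.** Protocol 10.0 defines an adverse event (AE) broadly, related or not, and then restricts what is collected: "Adverse Events will not be captured unless they are study related or the relationship is unable to be determined". It adds that "An Adverse Device Effect (ADE) is a study-related Adverse Event". An event whose relationship to the System "is not able to be determined, it will be captured on an Adverse Event Form and reported to the Sponsor".

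Protocol 9.5 appoints an independent reviewer to adjudicate study-related AEs. On what the reviewer knows, it says "AE information, including group assignment, will be provided to the Reviewer"; on the status of the decision, "The adjudication by the Clinical Events Reviewer will be the final determination".

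The primary safety endpoint (Protocol 4.4.1.2), the safety analysis in Protocol 8.3 and SAP 9.0 are all framed in terms of study-related events or ADEs. SAP 9.1 gives subject counts and percentages in these categories: "at least one ADE, serious ADE, unanticipated ADE, or ADE leading to death will be presented by treatment group".

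On knowledge of assignment, Protocol 5.2.1 conceals it from the subject and the blinded evaluator but makes it known to unblinded study staff. The week 3, 5 and 7 calls (Protocol 5.5, 5.7 and 5.9) are made by the unblinded evaluator.

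Protocol 5.0 says that adverse events are to be recorded throughout the study and attaches no relatedness condition.

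**The concern.** A concurrent sham arm lets event rates be compared without anyone having to decide what caused each event. If similar events occur at similar rates in both arms, the comparison itself shows it. That advantage is lost for any event screened out on attribution before it is written down, because neither the reviewer nor a later analyst can recover it.

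The screening judgement is also made in a trial where some of the people in contact with subjects know the arm. Someone who knows that no current was delivered may more readily rule out a stimulation cause. What is at stake is whether the two columns of the safety summary are comparable, and whether serious events in a randomised trial are counted completely. The efficacy analysis is not affected.

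**Working it through.** No arithmetic applies: the point concerns capture and reporting rules, and the documents give no event rates. The check follows each class of event, as first judged, through the rules.

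| Class at first judgement | Recorded (Protocol 10.0) | Seen by reviewer (Protocol 9.5) | In primary safety endpoint (Protocol 4.4.1.2, 8.3) | In SAP 9.1 summary |
|---|---|---|---|---|
| Related | Yes | Yes | Yes, subject to adjudication | Yes, subject to adjudication |
| Undetermined | Yes, on a form sent to the sponsor | Not stated; the remit names study-related events | Outside the ADE definition as written | Not named in the visible text |
| Unrelated | No | Not possible | No | No |

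1. The third row follows directly from the capture rule. It is a stated rule and not a silence in the documents. Nothing in it exempts serious events.
2. The reviewer's decision is final, but it operates only on what was recorded. For events first judged unrelated, there is nothing on which to be final.
3. The second row is a gap. If undetermined events go to the reviewer, some could be ruled related and would then count as ADEs. If they do not, the ADE definition leaves them outside the endpoint. The visible text does not say which.
4. On differences by arm, the lead-placement text after Protocol 5.2.1 says the procedure is the same in both groups apart from active stimulation. Events from leads or the procedure are therefore equally attributable in either arm. A differential filter is plausible mainly for events that might be attributed to stimulation.
5. Protocol 5.0 and Protocol 10.0 conflict. One has adverse events recorded without condition, and the other excludes those judged unrelated. The call 24 to 48 hours after lead placement (Protocol 5.2.9) asks only about ADEs, which fits the narrower rule.

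**The case against.** The strongest defence is that this is a post-market study of a cleared device whose stated safety endpoint is study-related events. Capture matches that endpoint, and events of uncertain relation are retained. That is a coherent choice, and SAP 9.1 shows a descriptive by-group summary with no test in the visible text. This limits the consequences, but it does not make an unrecorded event reviewable or restore a comparison free of attribution.

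Several stronger readings are tempting, and the documents do not support them:

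- **Undetermined events appear in no table.** This cannot be shown. The public text of SAP 9.0 breaks off mid-passage and a figure is missing after Protocol 8.3, so a summary of these events may be in removed text.
- **Adjudication can only lower the ADE count.** This fails if undetermined events reach the reviewer, who could rule them related.
- **Unblinded site staff make the first relatedness judgement.** That the site makes it is a fair inference, but no visible passage names who does. Sites have both blinded and unblinded staff (Protocol 7.6).
- **Collection of unrelated serious events varies by ethics board.** The sentence that "some IRBs will require that AEs that are serious in nature, even if not study related, will be reported as well" concerns what investigators report to their boards, not what enters the trial data.
- **The distortion can be quantified.** Any pair of recorded rates would rest wholly on assumed event rates and assumed losses per arm. If losses were greater under sham, the recorded comparison would make active treatment look worse, so even the direction is not settled against the sham arm.

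**Conclusion.** The point holds in this form. An AE judged unrelated, serious or not, is not recorded, cannot be reclassified by the independent reviewer and is absent from the by-group safety summary. Because assignment is known to some site staff and to the reviewer, the filter can act differently by arm, chiefly for events that might be attributed to stimulation. Its size and direction are unknown.

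The first part rests only on the text of Protocol 10.0 and 9.5 and SAP 9.1. The second part assumes that someone who knows the arm makes or influences the first judgement, which the documents allow but do not state. Two clarifications are also owed: how undetermined events are adjudicated and counted, and which of Protocol 5.0 and 10.0 governs recording. This is an inexpensive improvement worth making. It is not evidence that the safety results are wrong.

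**What to change.** - **Capture.** From Visit 2 to Visit 11, record every serious AE and every AE in the treated leg at all sites, regardless of judged relation. Visit 11 is the natural limit because sham subjects cross over or leave after it, which ends the randomised comparison.
- **Adjudication.** Send these events, and all events of undetermined relation, to the independent reviewer for the relatedness decision.
- **Reporting.** In SAP 9.1, summarise them by group alongside the ADE table. Show events still undetermined after review on a separate line, and add a sensitivity count that includes them as ADEs. The protocol's ADE definition and primary safety endpoint stay unchanged.
- **Consistency.** Reconcile Protocol 5.0 with Protocol 10.0. If removed text already covers undetermined events, confirm that and cross-refer to it.

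The cost is a protocol amendment, matching SAP text and some extra AE forms at contacts that already take place. No visits are added, and only recording changes. The reviewer would still know the arm, so the by-group table of events regardless of relation is the part that does not depend on attribution.

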### 11.0 Risk Benefit Analysis

The potential risks and benefits to study subjects participating in this study are listed below.

[figure not shown]
#### 11.1 Potential Benefits

Subjects in this study may not receive any direct benefit by participating in this study.

[figure not shown]
This research may benefit future patients with postoperative pain following knee replacement surgery.

[figure not shown]
### 11.2 Known and Anticipated Risks

[figure not shown]
The risks listed below are described as common or rare

[figure not shown]

[figure not shown]

[figure not shown]

[figure not shown]

[figure not shown]
# 11.3 Risk Analysis

As described above, all efforts will be made to mitigate each potential risk associated with the use of the system.

The potential risks of participation in this study have been minimized such that they are unlikely to occur and/or have non-serious consequences.

# 11.4 Risk Justification

The potential benefits of this procedure to reduce post-operative pain and opioid use following orthopedic surgery outweigh the risks associated with this procedure and temporary treatment.

[figure not shown]
### 12.0 Study Administration

#### 12.1 Record Retention

By signing the Investigator Agreement, the Investigator agrees to retain study-related documents in a secure location to which access can only be gained if required. Following study completion, the following documents will be archived: the study regulatory files containing all Essential documents, including signed Informed Consent forms, patient-related materials, and CRFs. The Investigator will be required to retain all records required by this study per their contract with the sponsor. The investigator must inform SPR Therapeutics if the location of the records changes or if there are any plans to destroy the records.

### 12.2 Criteria for Terminating a Subject

SPR Therapeutics reserves the right to terminate a study subject at any time. SPR Therapeutics only intends to exercise this right for valid scientific or administrative reasons, and reasons related to the protection of Human Subjects participating in this study.

### 12.3 Criteria for Terminating the Study

SPR Therapeutics reserves the right to terminate the study at any time. SPR Therapeutics only intends to exercise this right for valid scientific or administrative reasons, and reasons related to the protection of Human Subjects participating in this

[figure not shown]
### 12.4 Criteria for Terminating a Center

The Sponsor reserves the right to suspend or stop the enrollment of subjects at a study center at any time after the study initiation if no subjects have been enrolled or if enrollment numbers are well below anticipated enrollment expectations.

[figure not shown]
### 12.5 Investigator Qualifications, Responsibilities, and Training

To participate in this study, the Investigator must sign the Investigator Agreement which documents his responsibilities in the study. The Investigator will require training on this study plan and the device.

### 1.0 Version Control

This Statistical Analysis Plan (SAP) is based on study protocol

### 2.0 Objectives

The study objective is to gather post-market data regarding the safety and effectiveness of the peripheral nerve stimulation (PNS) therapy for the treatment of postoperative pain following knee replacement.

### 3.0 Study Design

[figure not shown]
The current study is a prospective randomized, double-blinded, placebo-controlled, multicenter study to gather data regarding the treatment of postoperative pain following orthopedic surgery (e.g., total knee replacement [TKR] and partial/unicompartmental knee replacement [PKR]; including unilateral and bilateral knee replacements and primary and revision knee replacements) with the PNS therapy. Details on study design can be found in the study protocol (0150-CSP-000).

#### 3.1 Randomization

Qualifying individuals will be randomized to either Group #1 (Treatment) or Group #2 (Control) using permuted-block randomization. Eligibility and the schedule and procedure for randomization are detailed in the study protocol (0150-CSP-000).

Subjects included in the primary endpoint analysis (subjects who have undergone a primary TKR) will be randomized separately from subjects in the exploratory analysis group (subjects who have undergone a PKR or secondary/revision TKR) to maintain an appropriate distribution for the primary endpoint analysis. Individuals will be blinded to their randomization assignment until the close of Visit 11 (3-mo after start of therapy).

3.2 Sample Size Rationale

### 4.0 Study Hypotheses

The primary hypothesis is tested under a significance level of 0.05 (two-sided). All secondary hypotheses are considered exploratory in nature and claims of statistical significance will not be made based on the statistical tests. Any hypotheses tested will be at a significance level of 0.05 (two-sided) with no adjustments for multiple comparisons. Primary, secondary, and exploratory endpoints are described in Section 5.0 (Endpoint Analyses) and Section 8.0 (Efficacy Analyses), including the data collection instruments, data analysis techniques (e.g., thresholds for success in a given outcome), and statistical tests for each endpoint.

### 4.1 Primary Hypothesis

Overall Proportion of Success in Group #1 (G1) with active PNS vs. Group #2 (G2) with sham PNS for reduction of postoperative pain following a primary total knee replacement orthopedic surgery. The null  $(H_0)$  and alternative hypotheses  $(H_a)$  are:

H0: 
$$p_{G1} - p_{G2} = 0$$
 vs.

Ha: 
$$p_{G1} - p_{G2} \neq 0$$

where p G1 and p G2 are the proportions of success in average pain intensity during Weeks 5-8 in active PNS Group #1 and sham PNS Group #2, respectively.

### 4.2 Secondary Hypotheses

The Secondary null  $(H_0)$  and alternative hypotheses  $(H_a)$  are:

1) Proportions of success in average pain intensity between groups for Weeks 1-4. The null (H0) and alternative hypotheses (Ha) are:

H0: 
$$p_{G1} - p_{G2} = 0$$
 vs.

Ha: 
$$p_{G1} - p_{G2} \neq 0$$

where p G1 and p G2 are the proportions of success for average pain intensity during Weeks 1-4 in Group #1 and during Weeks 1-4 in Group #2, respectively.

2) Proportions of success in average pain intensity (durability of primary endpoint) at 3, 6, 9, and 12 months after SOT

H0: 
$$p_{G1} - p_{G2} = 0$$
 vs.

$$H_a: p_{G1} - p_{G2} \neq 0$$

where p G1 and p G2 are the proportions of success for average pain intensity at follow up (3, 6, 9, and 12 months after SOT in Group #1 and 3 months after SOT in Group #2).

3) Mean average pain relief at specified intervals after start of therapy

H0: 
$$u_{G1} - u_{G2} = 0$$
 vs.

$$H_a$$
:  $u_{G1} - u_{G2} \neq 0$ 

where u G1 and u G2 are the mean percent improvement in average pain intensity at specified intervals after start of therapy (Weeks 1-4, Weeks 5-8, and 3, 6, 9, and 12

months after SOT in Group #1 and Weeks 1-4, Weeks 5-8, and 3 months after SOT in Group #2).

4) Pain medication usage at specified intervals after start of therapy (opioid, non-opioid and total analgesic medication usage analyzed separately)

H0: 
$$p_{G1} - p_{G2} = 0$$
 vs.

Ha: 
$$p_{G1} - p_{G2} \neq 0$$

where p G1 and p G2 are the distribution probabilities for pain medication usage at monthly intervals (Weeks 1-4, Weeks 5-8, and 3, 6, 9, and 12 months after SOT in Group #1 and Weeks 1-4, Weeks 5-8, and 3 months after SOT in Group #2).

5) Pain Catastrophizing Scale (PCS) at specified intervals after start of therapy

$$H_0$$
:  $u_{G1} - u_{G2} = 0$  vs.

$$H_a$$
:  $u_{G1} - u_{G2} \neq 0$ 

where u G1 and u G2 are the mean percent improvement in PCS at specified intervals after start of therapy (4 weeks, 8 weeks after SOT in Group #1 and 4 weeks, 8 weeks after SOT in Group #2).

6) Patient global impression of change (PGIC) at specified intervals after start of therapy

H0: 
$$u_{G1} - u_{G2} = 0$$
 vs.

Ha: 
$$u_{G1} - u_{G2} \neq 0$$

where u G1 and u G2 are the mean scores for PGIC at specified intervals after start of therapy (4 weeks, 8 weeks, and 3, 6, and 12 months after SOT in Group #1 and 4 weeks, 8 weeks, and 3 months after SOT in Group #2).

7) Pain Interference (BPI-9) at specified intervals after start of therapy

H0: 
$$p_{G1} - p_{G2} = 0$$
 vs.

Ha: 
$$p_{G1} - p_{G2} \neq 0$$

where p G1 and p G2 are the proportions of success for pain interference at specified intervals after start of therapy (4 weeks, 8 weeks, and 3, 6, 9, and 12 months after SOT in Group #1 and 4 weeks, 8 weeks, and 3 months after SOT in Group #2).

8) Physical recovery (Western Ontario and McMaster Universities Osteoarthritis Index; WOMAC) at specified intervals after start of therapy

$$H_0$$
:  $p_{G1} - p_{G2} = 0$  vs.

$$H_a$$
:  $p_{G1} - p_{G2} \neq 0$ 

where p G1 and p G2 are the proportions of success for WOMAC at specified intervals after start of therapy (8 weeks, and 3, 6, and 12 months after SOT in Group #1 and 8 weeks and 3 months after SOT in Group #2).

9) 6MWT at specified intervals after start of therapy

H0: 
$$u_{G1} - u_{G2} = 0$$
 vs.

Ha: 
$$u_{G1} - u_{G2} \neq 0$$

where u G1 and u G2 are the mean percent improvement on the 6MWT at specified intervals after start of therapy (8 weeks and 3 months after SOT).

### 5.0 Endpoint Analyses

Analyses of the primary and secondary effectiveness endpoints will be conducted on the full analysis set and the per-protocol population set at each specified study interval. The full analysis

set is considered the primary population for formal statistical hypothesis testing.
5.1 Primary Endpoint  Relief of postoperative pain will be evaluated using the average pain intensity. All subject will record pain scores daily for the qualifying knee (i.e., with total knee implant and qualifyin pain) in the 7-day diaries using BPI-SF Question #5. Data will be collected  Each subject must have ≥50% reduction is
pain relative to baseline to be considered a success in the primary efficacy endpoint analysis. Missing data will be handled according to Section 8.2. The primare endpoint analysis will be based upon the Full Analysis Set, including imputation for missing data due to missed visits and early termination. An analysis will also be performed based on the Perotocol population,
Group #1 will receive active stimulation and Group #2 wi receive sham stimulation during the 8-week home trial.
The primary endpoint compares the proportion of subjects in Group #1 relative to that in Group #2 that achieve $\geq 50\%$ reduction in pain from baseline to Weeks 5-8 of the home trial using Fisher's exact test. The null hypothesis (H 0 ) is that the PNS treatment (Group #1, activational stimulation) is equal to the control (Group #2, sham stimulation) in providing pain relief. The alternative hypothesis (H a ) is that Group #1 has a proportion of successes that is not equal to the

 $H_0$ : proportion of successes in Group #1 = proportion of successes in Group #2  $H_a$ : proportion of successes in Group #2  $\neq$  proportion of successes in Group #2

If the proportion of successes in the PNS treatment is larger than the proportion of successes in the control during the Weeks 5-8 of the home trial and statistically significantly different (p < 0.05, two-sided), then the null hypothesis is rejected at the 0.05 level of significance, which will indicate that the therapeutic effect is clinically significant and superior to the placebo effect[2].

proportion of successes in Group #2.

treatment effect for time from TKR.

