### 4.4.1 Primary Endpoints

### 4.4.1.1 Primary Efficacy Endpoint

The primary efficacy endpoint will be average post-operative pain, for primary TKR subjects only, in the affected knee from weeks 5-8 of the treatment period (in both Group #1 and Group #2) compared to baseline.

All subjects will record average knee pain scores (BPI-SF Question #5) for the affected knee in diaries Subjects will record one pain score per day. For each subject, the 7-day baseline diary collection period will be used to calculate the mean of the "average pain." Each randomized subject must obtain ≥ 50% reduction during weeks 5-8 of the treatment period relative to the baseline score to be considered a success.

The primary endpoint of the study compares the proportion of successes of Group #1 (Treatment) relative to that of Group #2 (Control),

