### 5.2.5 Pain Catastrophizing Scale (PCS) at 4 weeks and 8 weeks after SOT

PCS is a widely-used, validated 13-question instrument to assess rumination (4 questions), magnification (3 questions), and helplessness (6 questions). The survey asks participants to think back on painful experiences in the past and reflect on how often they had specific thoughts or feelings. Each question is scored on a 0-4 scale with 0 = "not at all" and 4 = "all the time". Higher scores indicate a greater tendency towards catastrophizing pain, which has been correlated with worse pain and response to pain therapies.

The analysis of treatment effect on PCS examines the difference in the mean percent improvement from baseline at specified intervals in Group #1 relative to that of Group #2. The baseline PCS score will be compared to the PCS score at the specified intervals after start of therapy. The mean percent improvement in Group #1 at 4 weeks and 8 weeks will be compared to

Group #2 at 4 weeks and 8 weeks, respectively. The difference between groups will be evaluated with a Wilcoxon rank-sum test. The null hypothesis is that there is no difference in mean percent improvement between the two treatment groups, versus the alternative hypothesis, that the mean percent improvements differ from one another. Testing will be conducted at the 0.05 level of significance.

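### The primary Fisher's exact test adjusts for no baseline covariate: baseline pain enters only through the responder definition, and baseline PCS enters no readable analysis of the primary outcome

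*SAP*

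**What the plan says.** - **Primary test.** SAP 5.1: "The primary endpoint compares the proportion of subjects in Group #1 relative to that in Group #2 that achieve" at least a 50% "reduction in pain from baseline to Weeks 5-8 of the home trial using Fisher's exact test". SAP 4.0 sets the level at 0.05, two-sided.
- **Baseline pain.** Under Protocol 4.4.1.1, "the 7-day baseline diary collection period will be used to calculate the mean of the" subject's average pain. The responder rule is relative to that mean: SAP 5.1 requires at least a 50% reduction in "pain relative to baseline to be considered a success in the primary efficacy endpoint analysis".
- **Baseline PCS.** SAP 5.2.5: "The baseline PCS score will be compared to the PCS score at the specified intervals after start of therapy". It describes a greater tendency to catastrophize as something "which has been correlated with worse pain and response to pain therapies". PCS is then used only as a secondary outcome at 4 and 8 weeks.
- **Other baseline factors.** SAP 5.1 ends with a cut-off sentence, "treatment effect for time from TKR", whose beginning cannot be read.
- **Regression of the primary outcome.** The one shown in full is in SAP 5.2.4, part 2. It contains treatment and change in medication, and it is stated not to affect the primary result.
- **Randomization.** SAP 3.1 describes permuted blocks, with primary TKR subjects randomized separately from the PKR and revision subjects. The readable text names no stratification by baseline pain or PCS.

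**The concern.** The SAP itself names a baseline variable that it regards as related to treatment response, and collects it, yet does not use it in the readable analysis of the primary outcome. Baseline pain is in the responder definition, but dividing by baseline is not the same as adjusting for it, because the chance of a 50% reduction can still depend on where the subject started. The medication regression does not fill the gap, since medication change is measured after randomization.

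Two things are at stake, both about the effect estimate. Prognostic information that could narrow its confidence interval goes unused. And if the arms differ by chance in baseline pain or PCS, no readable prespecified estimate allows for it, which invites covariate selection after the data are seen.

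**Working it through.** **What can be reproduced.** Sample size, power, assumed response rates and allocation ratio are withheld, so there is no plan figure to reproduce. Everything below rests on assumptions: 1:1 allocation, 30 to 50 per arm, and success of 60% v 30%.

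**1. Precision of the crude risk difference.** SE = sqrt[p1(1-p1)/n + p2(1-p2)/n] = sqrt[(0.24 + 0.21)/n].
- 30 per arm: sqrt(0.45/30) = 0.1225, 95% CI half-width 1.96 × 0.1225 = 24.0 points.
- 50 per arm: sqrt(0.45/50) = 0.0949, half-width 18.6 points.

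**2. Precision after adjustment.** Trials were simulated with a latent-normal binary outcome, 4,000 per cell. The crude difference was compared with the standardised risk difference from a logistic model with treatment and baseline covariates. Change in standard error, approximate and subject to simulation error:

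| Latent variance explained | Change in SE, 30-50 per arm |
|---|---|
| 0% | +1 to +2% |
| 10% | -1 to -2% |
| 20% | -3 to -6% |
| 30% | -6 to -8% |

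The mean estimate was about 0.30 throughout, so the method showed no bias.

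**3. What those percentages mean.** At 30 per arm, a 1% reduction takes the half-width from 24.0 to 24.0 × 0.99 = 23.8 points, and an 8% reduction takes it to 24.0 × 0.92 = 22.1. In equivalent sample size, 1/0.99² = 1.02 (2% more subjects) and 1/0.92² = 1.18 (18% more). A 2% rise gives 1/1.02² = 0.96 (4% fewer).

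**4. Chance imbalance.** The SE of a standardised baseline difference is sqrt(2/n). At 30 per arm it is sqrt(2/30) = 0.258 SD, and 0.5/0.258 = 1.94, so about 5% of trials have an imbalance of at least 0.5 SD in any one covariate. The same formula gives 7.7% at 25 per arm and 1.2% at 50.

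**5. What such an imbalance could do.** Suppose one covariate explains 20% of latent variance and the success rate is 30% (normal quantile -0.524). A 0.5 SD imbalance shifts the latent mean by 0.5 × sqrt(0.20) = 0.224. Then Φ(-0.524 + 0.224) = Φ(-0.300) = 0.38, a difference of about 8 points unrelated to treatment.

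**6. Validity of the existing test.** By exact enumeration at a common 30% success rate, Fisher's test rejects in 2.3%, 2.8% and 3.1% of trials at 25, 35 and 50 per arm, all below the nominal 5%. Its exact power at 60% v 30% is 51%, 62% and 83%. Reporting an adjusted estimate beside it changes none of these figures.

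**The case against.** The strongest reply is that an unadjusted exact test in a randomized trial is a legitimate choice. It is valid, and if anything conservative. The gain from adjustment may be negligible: SAP 5.2.5 says only that there is a correlation and gives no strength, and it also ties catastrophizing to worse pain, so PCS and baseline pain partly carry the same information. The baseline pain floor in Protocol 4.2.1.2 narrows the range of one covariate. A model also spends information: at 30 per arm and 60% v 30% there are 18 + 9 = 27 successes for treatment, two or three covariates and an intercept. All of this stands. It is why the point concerns the estimate and not the test.

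Four stronger readings are tempting, and the documents do not support them:
- *The comparison ignores baseline pain.* It does not. The baseline diary mean is the denominator of the responder definition. It is absent only as a covariate.
- *The primary result is biased or its error rate inflated.* Randomization protects the comparison, and step 6 shows rejection rates below 5%.
- *Adjustment would raise the power of the confirmatory test.* An adjusted logistic likelihood-ratio test can show higher power, but that is a different test. In simulations at 20% v 50% with 25 to 50 per arm, most of its advantage over Fisher came from leaving the exact test. The covariates added about 0 to 7 points over an unadjusted chi-square, and its null rejection was 4.8-6.6%. With Fisher's test kept, its power stays as it is.
- *The plan contains no adjusted analysis.* This cannot be said. The contents of SAP 8.0 and 8.2, SAP 5.2.10 and most of Protocol 8.0 are not shown. The time-from-TKR sentence suggests that some analysis of a baseline factor exists. Stratification factors may also lie in missing text after the block randomization statement in Protocol 5.2.1.

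**Conclusion.** The point holds as a modest one about precision and prespecification. The readable primary test is unadjusted, both covariates are already collected, and the SAP itself gives the reason to consider PCS. Under the assumed 60% v 30% success and 30-50 per arm, the gain ranges from about 1-2% off the standard error at 10% of latent variance explained to about 6-8% at 30%, with a loss of about 1-2% if the covariates carry no information. The documents do not show where in that range this trial lies. Protection against imbalance matters most if the arms are small: an imbalance of at least 0.5 SD in a given covariate is expected in about 5% of trials at 30 per arm but only 1.2% at 50. Withheld text may already hold a supportive adjusted model. That would change what needs to be added, but not the readable primary test.

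**What to change.** Keep Fisher's exact test for the confirmatory p-value. Beside it, prespecify a covariate-standardised risk difference with 95% CI from a logistic model with treatment, baseline 7-day diary mean and baseline PCS. Enter both covariates as continuous and fix the model before unblinding. Add time from TKR if the partly unreadable analysis in SAP 5.1 already adjusts for it. If the withheld text already contains an adjusted model of the primary outcome, it is enough to confirm that it includes these two covariates.

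The cost is SAP wording and one model; both covariates are already collected. The downsides are a modelling assumption, a slight loss of precision if the covariates turn out not to be prognostic, and an adjusted estimate that can differ slightly from the crude difference. The SAP should therefore say in advance that the confirmatory decision rests on Fisher's test.
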